Effects of Photobiomodulation on Postoperative Pain After Primary Endodontic Therapy in Molars With Symptomatic Apical Periodontitis

NCT05032612

Version Date: 9/14/2021

Protocol Title: Effects of photobiomodulation on postoperative pain after primary endodontic therapy in mandibular molars with symptomatic apical periodontitis

Principal Investigator: [name]

Co-Investigators: [name], [name], [name], [name].

Population: Sample size = 52 adult patients ages 18 and older divided into two groups (intervention group and control group)

Number of Sites: 1 site; UT School of Dentistry Graduate Endodontic Clinic

Study Duration: One year - Two academic semesters

Subject Duration: One dental visit - approximately 2 hours

General Information

Teeth diagnosed with SAP are more prone to present postoperative pain even after root canal therapy (RCT) is completed. Photobiomodulation (PBM) has been used for decades in medicine and dentistry showing promise results in the healing capabilities, however, an accepted protocol has still not been created for its regular use in endodontics. PBM utilizes the body's own hardware by working specifically on the mitochondria in cells to improve patient healing and reduce post-treatment pain. The mitochondrial events taking place during PBM are thought to be: increased ATP production, release of nitric oxide, and release of reactive oxygen species. All of these events lead to an increase in cellular mediators involved in inflammation and pain control and thus PBM can greatly improve the outcomes of our endodontic treatment on these teeth.

The aim of this clinical study is to investigate the use of PBM after primary root canal therapy in mandibular molars diagnosed with symptomatic apical periodontitis (SAP) to reduce postoperative pain.

Fifty-two adult patients will be invited to participate in this study. They will be divided in 2 groups: Control group where patients will receive conventional RCT (n=26) and PBM group where patients will receive conventional RCT plus PBM immediately post-operatively (n=26). Pre-operative and postoperative pain will be accessed by using a visual analogue pain scale. Data will be analyzed using continuous ordinal regression and distribution-free methods (Wilcoxon, Mann-Whitney tests)

Background Information

One of the main goals of endodontic (root canal) therapy is to eliminate pain. It has been well described in the literature that certain teeth tend to hurt more after root canal therapy.

Preoperative pain intensity, pain interfering with daily activities, pain made worse with stress,

and diagnosis of symptomatic apical periodontitis were all listed as independent predictors of severe pain intensity following root canal therapy (Law et al, 2015). Another study looked at similar predictors of postoperative pain and found mandibular molars to have significantly more postoperative pain than maxillary molars (Sadaf, 2014).

Our everyday options for post-treatment pain is mostly limited to various prescription medications. This should be considered a major limitation especially in today's world where we are fighting an active opioid crisis.

According to the CDC, from 1999-2019 nearly 841,000 people died from an overdose involving prescription and illicit opioids. Nearly 247,000 Americans lost their lives to overdoses involving prescription opioids in the same two-decade time period. The good news is that the trend is now declining and doctors are prescribing opioids with much more caution. From 2006-2017 there was a 19% reduction in annual prescribing of opioids but the amount of opioids in morphine milligram equivalents (MME) prescribed per person is still around 3x what it was in 1999.

Today, we know through an overwhelming amount of evidence that NSAIDS, Acetaminophen, and long-acting local anesthetics may result in greater analgesia for our patients than opioids. Acetaminophen and NSAIDS are great in dealing with pain, however their effectiveness is rather limited. Both Acetaminophen and NSAIDS are subject to a ceiling dosage with regard to effective analgesia. This means that past a certain dosage, the patient cannot achieve any greater pain relief than what was provided before they reached that ceiling dose. The point is – there are dozens of unique situations where practitioners need to have more tools available in dealing with pain when the standard protocol is ineffective.

One such way of dealing with this pain is using Photobiomodulation (PBM), also known as low-level light therapy (LLLT), to deal with post-treatment pain. Photobiomodulation's effects on accelerating the healing process were introduced in the 1960s but its use in dentistry is still not all that commonplace. The generally accepted mechanism of action is that absorbed light from the laser on the target tissue creates reactive oxygen species which leads to gene transcription and cellular healing. Mitochondria are very receptive to this process and the near-infrared light is absorbed and the energy is converted into ATP for cellular functions. Cytochrome C is key to this process as it is a chromophore and accepts the light to move these processes forward—at least that is the current level of thinking on the subject. There have been many studies showing the effects of PBM on healing in various medical specialties including dentistry but an accepted protocol has not yet been standardized. The Grotthus-Draper law or law of photochemical activation states that only light which is absorbed by a system can bring about a photochemical change. The correct wavelength for the target cells chromophores to induce the desired effect of PBM is 633 – 830 nm according to Kim and Calderhead. In this study, we will be using 660 nm to achieve our desired and expected results with PBM.

Objective:

The aim of this study is to evaluate the effects of photobiomodulation (PBM) on postoperative pain after endodontic treatment in mandibular molar teeth diagnosed with symptomatic apical periodontitis.

Study Design:

This randomized clinical trial is designed to evaluate the effects of photobiomodulation (PBM) on patients with symptomatic apical periodontitis (SAP) receiving root canal therapy.

Fifty-two patients (n=52) diagnosed with SAP will be selected and invited to participate in the study.

The inclusion criteria:

- Patients over 18 years old
- Posterior mandibular molars
- No previous root canal therapy on the tooth in question
- Able to complete the endodontic treatment in one visit

The exclusion criteria:

- Maxillary teeth, mandibular anteriors and premolars
- Infection (swelling, sinus tract) on the tooth in question
- Periodontal disease on the tooth in question
- Dental trauma
- Crown/ root fractures
- Bone marrow transplant or other organ transplant patients who are on chemical immunosuppressants
- Uncontrolled HIV disease
- Patients at risk for delayed or compromised wound healing

Note: Patients who are HIV positive and taking ART with undetectable viral load and a CD4 cell count above 400 are not considered immunocompromised

The group distribution treatment will be done by the investigators by computer-generated randomization (Research Randomizer). Patients will be randomly divided into two groups:

- (A) experimental group - patients will receive root canal and PBM treatment.
- (B) control group - patients will receive root canal and PBM sham treatment.

Patients will be informed of the details of study procedures. They will have the opportunity to ask questions. The consent form will be presented and discussed with patients and should be signed before the procedure. A single calibrated operator will perform all of the treatments (root canal therapy, PBM, and PBM sham treatments).

Pre-treatment pain assessment

The operator will ask the patient to rate pain level before starting the endodontic treatment.

A Visual Analogue Scale (VAS) will be provided to the patient and is used as a pictorial tool to help patients quantify their pain level: 1-3 = mild pain; 4-6 = moderate pain; 7-10 = severe pain. (Figure 1)

[figure not shown]

Figure 1. Illustration of the Visual Analogue Scale (VAS).

Endodontic Treatment

Patients will be anesthetized using 1.76 ml of 0.5% marcaine with 1:200,000 epinephrine via inferior alveolar nerve block, 1.76 mL 2% lidocaine with 1:100,000 epinephrine via inferior alveolar nerve block, and 1.76 mL of 4% Articaine with 1:200,000 epinephrine via infiltration.

Conventional endodontic treatment will be performed as follows: radiographs, dental dam isolation, straight-line access, cavity preparation, working length determined using an electronic apex locator, and a #10 K file. Canals will be prepared using Vortex Blue rotary instrumentation with 0.04 taper according to manufacturer's instructions and the #10 K file used for patency at the beginning of the procedure.

Irrigation will be performed with 10 mL of 6% sodium hypochlorite with in-and-out pecking motions, and a final rinse using 5 mL of 17% EDTA for 1 minute followed by 4 mL of 6% NaOCl for 1 minute. Irrigant activation will be completed prior to final rinse using an XP Endo Finisher (FKG Dentaire, La-Chaux-de-Fonds, Switzerland) file for 60 seconds using slight in-and-out movements.

After root canal preparation, the root canals will be dried with paper points and filled using matched single cones and CeraSeal(MetaBiomed, America) – a calcium silicate-based sealer. Final radiograph will confirm final canals obturation.

The pulp chamber will be etched with 35% phosphoric acid for 15 seconds, rinsed and gently dried, bonding agent (OptiBond® Solo Plus™, Kerr Corporation, Brea, CA, USA) will be applied, gently air-dried and light-cured for 20 seconds. Permaflo purple (Ultradent, America) composite resin will be used to seal the canals and light-cure for 20 seconds. Tooth will be restored with a glass ionomer (Fuji IX, GC America, USA) to seal the access cavity using a bulk fill technique.

Photobiomodulation Treatment

Immediately after the endodontic treatment, PBM therapy or sham will be performed using a 660 nm diode laser (SiroLaser Advance Plus, Dentsply Sirona Inc, Charlotte, NC, USA), with an 8mm tip diameter. The laser tip will be placed on the following external surfaces in a contact mode: mesiobuccal, distobuccal, mesiolingual and distolingual (Figure 1). The power output of the laser will be 50mW and will be verified by Power Meter (PM600 Power/Energy meter,

Molelectron Detector Inc, Portland, OR, USA). Each site will be irradiated for 25 s with an energy density of 10 J/cm².

For the PBM sham similar procedure will be performed without activating the laser.

Figure 2. Illustration of laser tip positioning

Patient Dismissal

At the completion of treatment, patients will be given both verbal and written post-op instructions along with a pain diary form to be completed at home (Figure 3). No pain measurement will be taken after the procedure as the patient is anesthetized. Assuming no contraindications patients will be instructed to take 400 mg Ibuprofen with 500mg extra strength Tylenol as needed for pain. If another pain medication is to be administered the reason will be well documented and the patients VAS scores may be excluded as this could be a potential confounding variable. All dosages of pain medication will be recorded.

If patients are experiencing severe pain it will be recommended to take 400 mg Ibuprofen with 500 mg extra strength Tylenol. If a subject cannot be reached at a specific time point they will simply be asked to recall to the best of their ability their pain score at that time level when they are reached. If a patient continually cannot recall their VAS score or stops responding their data will be excluded.

[figure not shown]
Outcome Measures

Patient pain as assessed by score on pain scale (see visual analog scale below), end of follow up period is 6 months. Patients will be asked for their pain scale responses at 6 hr, 12hr, 24hr, and 72 hrs after treatment is completed.

Primary outcome measure: Patient pain as assessed by score on pain visual analogue scale at 72 hours

Secondary outcome measures: Patient pain as assessed by score on pain visual analogue scale at 6hrs, 12hrs, 24hrs

PAIN DIARY FORM

Timeline	Date & Hour	Pain Level - VAS	Pain medication & dosage
Prior to RCT			
6 hrs. after RCT			
12 hrs. after RCT			
24 hrs. after RCT			
72 hrs. after RCT			

Figure 3. Pain Diary Form to be completed by the patient at home.

Post-treatment pain assessment

Patients will be contacted via phone at 6, 12, 24, and 72-hour intervals. The pain level will be recorded by a blinded investigator. In addition, patients will be asked to self-report any pain medication intake.

Risks and benefits

Risks are minimal as photobiomodulation has not been shown to have any negative effects on the teeth and it potentially can reduce pain and improve healing after root canal therapy.

Photobiomodulation will be performed using a 660nm red laser, which may have eye hazard risks. All safety protocols will be followed including laser safety wavelength-specific goggles by everyone in the operatory including the patient. The operator is laser certified and has been trained in laser safety protocols.

Study Population

Patients, 18 years and older, with symptomatic apical periodontitis (SAP) receiving endodontic treatment in one visit from the UT Health Science Center, Graduate Endodontic Dental Clinic.

Data and Safety Monitoring

No adverse effects are expected. All patients will be de-identified. During the study, data will be securely stored on encrypted computers or in a locked file cabinet with access limited to study personnel. Subject confidentiality and anonymity will be maintained throughout the study.

Statistics

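### Pre-treatment pain is named as a predictor and recorded for every patient, but the stated analysis of 72-hour pain does not adjust for it

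*Combined protocol and SAP*

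**What the plan says.** **Predictor.** Background Information begins its list of predictors with "Preoperative pain intensity, pain interfering with daily activities, pain made worse with stress". These, together with the diagnosis of symptomatic apical periodontitis, "were all listed as independent predictors of severe pain intensity following root canal therapy". The diagnosis defines the study population. Preoperative pain is left free: the eligibility criteria set no minimum or maximum score.

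**Measurement.** Under Pre-treatment pain assessment, "The operator will ask the patient to rate pain level before starting the endodontic treatment". The scale is banded as "1-3 = mild pain; 4-6 = moderate pain; 7-10 = severe pain". The pain diary also has a row for the time before the root canal.

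**Allocation.** Study Design says "The group distribution treatment will be done by the investigators by computer-generated randomization (Research Randomizer" and that patients go at random into two groups. It names no strata, blocks or minimisation factors. General Information gives the sizes: "Control group where patients will receive conventional RCT (n=26) and PBM group where patients will receive conventional RCT plus PBM immediately post-operatively (n=26".

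**Analysis.** General Information names continuous ordinal regression and the Wilcoxon and Mann-Whitney tests. Statistics adds a 95% confidence interval of the mean for each group and a 0.05 significance level. Neither section names a baseline covariate. The primary outcome is the VAS score at 72 hours.

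**The concern.** The plan identifies a prognostic variable, collects it from everyone, and then gives it no stated role in either design or analysis. In a trial of 52 patients this has two consequences.

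- **Precision.** Variation in 72-hour pain that the baseline score could explain stays in the error term, so the treatment difference is estimated less precisely than the data allow.
- **Conditional bias.** If one arm happens to start in more pain, an unadjusted comparison passes part of that difference on to the 72-hour result. Averaged over all possible randomisations this cancels out. In the one randomisation that is carried out it need not.

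**Working it through.** The plan's N of 52 cannot be reproduced, because no effect size, SD or power is given. For orientation, 26 per arm at two-sided 5% (sidedness assumed) gives 80% power for (1.96 + 0.84) × √(2/26) = 0.78 SD.

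**Inputs.** From the documents: 26 per arm, 0.05 level, 72-hour VAS as the primary outcome. Assumed, because the documents give neither: a baseline VAS SD of 1.5 to 3 points, and a baseline-to-72-hour correlation r of 0.2 to 0.6.

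**1. Chance imbalance at baseline.** SE of the baseline difference = SD × √(1/26 + 1/26) = 0.277 × SD. P(difference of at least 1 point, either direction) = 2 × [1 − Φ(1/SE)].

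| Assumed SD | SE | 95% chance range | P(at least 1 point) |
|---|---|---|---|
| 1.5 | 0.416 | ±0.82 | 1.6% |
| 2.0 | 0.555 | ±1.09 | 7.1% |
| 2.5 | 0.693 | ±1.36 | 14.9% |
| 3.0 | 0.832 | ±1.63 | 22.9% |

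One point lies within the 95% chance range once the SD reaches 1/(1.96 × 0.277) = 1.84.

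**2. What a one-point imbalance does to an unadjusted comparison.** With equal SDs at baseline and 72 hours, the expected shift is r × 1 point: 0.2, 0.3 and 0.5 points for r = 0.2, 0.3 and 0.5. Given that imbalance, the unadjusted test's conditional type I error is 6.0%, 7.3% and 11.1% at SD 2, and 5.5%, 6.1% and 7.7% at SD 2.5. The unconditional error remains 5%.

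**3. What adjustment gains.** In a linear model with one baseline covariate and 52 patients, the variance of the treatment difference relative to the unadjusted one is about (1 − r²) × (1 + 1/48). The second factor is the cost of estimating the slope.

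| r | Relative variance | Reduction |
|---|---|---|
| 0.2 | 0.96 × 1.021 = 0.980 | 2% |
| 0.3 | 0.91 × 1.021 = 0.929 | 7% |
| 0.5 | 0.75 × 1.021 = 0.766 | 23% |
| 0.6 | 0.64 × 1.021 = 0.653 | 35% |

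Simulation with baseline mean 5.5 and SD 2.3 and 72-hour SD 2.2 (all assumed) gives about 7%, 22% and 35% for r = 0.3, 0.5 and 0.6.

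**4. What stratifying would add.** Under the same assumptions, blocks of 4 within the three bands cut the SD of the baseline imbalance from about 0.62 to 0.29 points. For the treatment difference, however, 12,000 simulated trials gave these variances relative to unstratified and unadjusted:

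| Approach | r = 0.3 | r = 0.5 | r = 0.6 |
|---|---|---|---|
| Stratified, band-adjusted | 0.947 | 0.794 | 0.709 |
| Unstratified, continuous VAS as covariate | 0.927 | 0.770 | 0.661 |
| Stratified, continuous VAS as covariate | 0.936 | 0.754 | 0.652 |

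The covariate alone does better than stratifying with band adjustment. Stratifying on top of the covariate moves the result by no more than about two percentage points in either direction. That agrees with the formula: perfect balance could remove only the 1/48 term, about 2%.

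**The case against.** **Unstratified randomisation is valid.** This stands. It protects the overall type I error, and most randomisations avoid a one-point imbalance even at the larger SDs.

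**A regression is already planned.** This stands in part. Continuous ordinal regression can carry a baseline term and may have been meant to. The plan does not say so, and it does not say whether the regression or the Mann-Whitney test decides the primary outcome.

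**The predictor's strength for this outcome is unknown.** This stands. It is cited for severe pain after root canal therapy. No correlation with 72-hour VAS is given, and by 72 hours it may be weak.

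**Stronger readings that the documents do not support.**
- A reader might infer that the randomisation is defective and must be stratified. The gain comes almost entirely from adjustment. Small blocks within three small strata also carry a risk here: the single operator takes the baseline score, delivers laser or sham, and so knows past assignments. No concealment procedure is described.
- A reader might infer a single unblocked list. The text names the tool and is silent on blocks and on the number of lists.
- A reader might call preoperative pain the strongest predictor. It comes first in a list that is not ranked.
- A reader might conclude that an imbalance could not be told apart from a treatment effect. Baseline scores are collected, so an imbalance would be visible and could be adjusted for afterwards. The weakness is that this would not be prespecified.

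**Conclusion.** The point holds as a gap in the analysis specification. A named and recorded predictor has no stated place in the comparison of 72-hour pain. The cost is lost precision, and bias conditional on an unlucky draw; it is not invalidity.

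A one-point baseline difference is possible rather than likely: from about 2% at SD 1.5 to 23% at SD 3. Adjustment is worth about 7% to 35% of the variance for r between 0.3 and 0.6, and little or nothing at 0.2. The SDs and correlations are assumptions. The variance figures come from a linear model, so for ordinal regression they indicate the order of the gain and are not exact. The recommendation does not depend on which values are right, because the score is already collected and the loss from adjusting for a useless covariate is only about 2% of the variance.

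**What to change.** In General Information and in Statistics, state that the primary between-arm comparison of 72-hour VAS is the continuous ordinal regression already named, with treatment arm and continuous pre-treatment VAS as terms. Report the adjusted treatment effect with its 95% confidence interval, and the unadjusted Mann-Whitney test as supportive. Use the score itself and not the three bands: this keeps more information and avoids deciding where a score of 0 belongs, since the printed bands start at 1.

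The cost is a sentence or two in each section and one extra model parameter, with no new patients, visits or measurements. One consequence should be written down: the ordinal-regression effect is then conditional on baseline pain and is not the same quantity as an unadjusted one.

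Stratifying by pain band is optional. If the sponsor wants it, the score must be recorded before assignment, the allocation must be concealed from the operator, and block sizes should vary and stay undisclosed. The arms might then end slightly off 26 and 26. The adjusted analysis is needed either way.

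### The stated laser dose of 10 J/cm² per site is about four times what the stated power, time and tip size deliver (about 2.5 J/cm²)

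*Combined protocol and SAP*

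**What the plan says.** The Photobiomodulation Treatment section gives every laser setting in one paragraph. The device is a 660 nm diode laser "with an 8mm tip diameter", applied in contact at four named surfaces of the tooth: two buccal and two lingual. On power it says "The power output of the laser will be 50mW and will be verified by Power Meter". On time and dose it says "Each site will be irradiated for 25 s with an energy density of 10 J/cm²". No separate beam or spot size is given, and no energy in joules.

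The control arm differs only in that the laser stays off: "For the PBM sham similar procedure will be performed without activating the laser". Under Study Design, "A single calibrated operator will perform all of the treatments", both active and sham. The Background Information says of this therapy that "an accepted protocol has not yet been standardized".

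**The concern.** Power, time, area and energy density are tied by one formula, so any three of them fix the fourth. The paragraph states power, time and energy density, and its only dimension is the tip diameter. With that diameter, the four figures cannot all be right.

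The laser exposure is the only planned difference between the arms, so its dose defines the treatment being tested. The protocol itself says the field has no settled dosing, and it plans journal submission, so readers are likely to rely on the dose stated here. There are two cases:

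- **The operator follows power and time.** Every active patient gets the same exposure, but it would be reported at about four times its real energy density. A later user could copy the wrong dose.
- **10 J/cm² is the real target.** The stated power and time deliver about a quarter of it over an 8 mm spot. A null result could then be read as a failure of a dose that was never given.

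The documents do not show which case applies.

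**Working it through.** **Inputs** (all from Photobiomodulation Treatment): power 50 mW = 0.050 W; time 25 s per site; tip diameter 8 mm, in contact; four sites; stated energy density 10 J/cm² per site.

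**Assumption:** the beam is circular and fills the 8 mm tip. The protocol gives no other dimension. Step 4 varies this.

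**1. Energy.** Energy = power × time = 0.050 × 25 = 1.25 J per site. Over four sites this is 4 × 1.25 = 5 J, in 4 × 25 = 100 s. Neither result depends on spot size.

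**2. Area.** π × (diameter/2)² = π × (0.4 cm)² = 0.5027 cm².

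**3. Energy density.** 1.25 / 0.5027 = 2.49 J/cm² per site. The stated 10 J/cm² is not reproduced: 10 / 2.487 = 4.02.

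**4. Narrower beam.** The same 1.25 J over smaller spots:

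| Spot diameter | Area (cm²) | J/cm² | Stated ÷ computed |
|---|---|---|---|
| 8 mm | 0.5027 | 2.49 | 4.02 |
| 7 mm | 0.3848 | 3.25 | 3.08 |
| 6 mm | 0.2827 | 4.42 | 2.26 |
| 5 mm | 0.1963 | 6.37 | 1.57 |
| 4 mm | 0.1257 | 9.95 | 1.01 |

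Exactly 10 J/cm² needs an area of 1.25 / 10 = 0.125 cm², which is a diameter of 3.99 mm.

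**5. Other readings.**

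- Taking 8 mm as a radius gives 0.62 J/cm².
- Taking an 8 mm square spot gives 1.25 / 0.64 = 1.95 J/cm².
- Adding the four site densities gives 4 × 2.487 = 9.95. This is not a true energy density, because 5 J over the combined area of 4 × 0.5027 = 2.01 cm² is still 2.49 J/cm².

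**6. What 10 J/cm² over 8 mm would need.**

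- Energy: 10 × 0.5027 = 5.03 J per site, or 20.1 J per tooth.
- Time at 50 mW: 5.03 / 0.050 = about 100.5 s per site, or 402 s in all.
- Power for 25 s: 5.03 / 25 = 0.201 W, about 201 mW.

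**The case against.** The strongest objection is that a tip diameter is not a beam diameter. Energy density depends on the irradiated area, which the protocol does not give. If the beam were about 4 mm wide, the 10 J/cm² would be right and only a spot size would be missing. This stands as a limit on the factor of four, which is conditional on a filled tip. It does not clear the text: 5, 6 and 7 mm spots all leave a gap, and a 4 mm spot would still have to be stated for anyone to reproduce the dose.

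A second reading is that 10 J/cm² is a cumulative figure, since the four site values add to 9.95. That may be how the number arose, but the sentence attaches it to each site, and densities at separate sites do not add.

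Third, the treatment can be carried out from power, time and site alone. The power is metered and one operator treats everyone, so 1.25 J per site is delivered whatever the spot size. A reader could also recompute the density from the settings printed beside it. All of this is true, and it means the exposure would be consistent across patients if the operator follows those settings. It does not show that this is the intended dose, and the meter, as described, checks power rather than area or energy density.

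Finally, no statistical property of the trial changes, and nothing in the documents shows that 2.5 rather than 10 J/cm² would alter the effect. That is conceded, and it leaves the urgency open to debate.

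**Conclusion.** The concern holds. Taking the beam to fill the 8 mm tip, the stated settings deliver 2.49 J/cm² per site against a stated 10 J/cm², a ratio of 4.02. The ratio falls to 2.26 for a 6 mm spot and 1.57 for a 5 mm spot, and disappears only at about 4 mm. Nothing else in the documents reconciles the figures.

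The two possible treatments differ materially: 5 J per tooth if power and time govern, or 20.1 J per tooth if 10 J/cm² over 8 mm governs. The documents cannot say which figure is wrong. The harm is to what dose the result can be said to support. Because that dose defines the tested intervention, it should be settled before patients are treated.

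**What to change.** Confirm the effective spot area from the device manual, then correct whichever figure is wrong. The choice is for the investigators.

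- **(a) 50 mW, 25 s and 8 mm are right.** Restate the dose as 1.25 J and about 2.5 J/cm² per site, 5 J in total over four sites. Cost: a manual check and one corrected sentence.
- **(b) 10 J/cm² per site over 8 mm is confirmed as the target.** Either lengthen the exposure to about 100 s per site, with the sham held for the same time, or raise the power to about 201 mW. The longer exposure adds 402 − 100 = 302 s, about 5 minutes per visit in both arms. The higher power requires confirming that the device can deliver it at 660 nm.
- **(c) The true spot is about 4 mm.** Correct the stated diameter. Cost: as for (a).

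In every case, state the spot area and report energy per site in joules alongside energy density. No option needs extra patients. Recording the delivered dose for each patient would be useful but is optional.

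### Scores of randomised, treated patients may be dropped at discretion once another pain medication is given, with no rule for when, by whom or on what basis

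*Combined protocol and SAP*

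**What the plan says.** Patient Dismissal gives the standard analgesic instruction: "Assuming no contraindications patients will be instructed to take 400 mg Ibuprofen with 500mg extra strength Tylenol as needed for pain". The next sentence is the rule at issue: "If another pain medication is to be administered the reason will be well documented and the patients VAS scores may be excluded". The stated rationale is that the other drug might confound the result. Later in the same section, patients in severe pain are advised to take the same two drugs at the same doses.

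Outcome Measures sets the endpoint: "Primary outcome measure: Patient pain as assessed by score on pain visual analogue scale at 72 hours". The 6-, 12- and 24-hour scores are secondary.

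Medication use is captured. Patient Dismissal says "All dosages of pain medication will be recorded", Post-treatment pain assessment says "patients will be asked to self-report any pain medication intake", and the diary has a column for drug and dose.

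For the analysis, General Information names continuous ordinal regression and "distribution-free methods (Wilcoxon, Mann-Whitney tests"), and Statistics adds confidence intervals for group means and a 0.05 significance level. Neither section defines who is analysed or how scores after another analgesic are handled.

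**The concern.** The named analgesics are taken as needed, so a patient who goes on to another drug after leaving the clinic will often do so because of pain. Pain is the outcome. If PBM works, fewer PBM than sham patients should need another drug, so dropping those scores removes high values unevenly and compares groups that are no longer the randomised ones. Calling the other drug a confounder does not justify this, because analgesic use after treatment is a possible consequence of treatment and not a baseline imbalance.

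The permissive wording adds a second problem. Nothing prevents a decision from being made after the scores are known, or with knowledge of allocation. It is also unclear whether all of a patient's scores go or only the later ones. With 26 per arm, a few such decisions could matter.

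**Working it through.** **1. Order of events.** Study Design describes randomisation without giving its exact moment. Photobiomodulation Treatment has PBM or sham delivered straight after the root canal, and dismissal follows. Allocation therefore precedes any use of the exclusion rule.

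**2. Two routes into the rule.**
- *Substitution at dismissal.* The patient cannot take one of the named drugs and is given another. The patient is still anaesthetised and no postoperative score exists. The trigger is a baseline trait, balanced between arms in expectation.
- *Pain at home.* The patient takes another drug because of pain. The trigger is related to the outcome and possibly to treatment.

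**3. Size.** The plan has no figure of its own to reproduce: 52 patients are stated without an effect size, SD or power. Everything below is illustration. Assumptions: control mean 4, PBM mean 3, SD 2, 26 per arm, two-sided 0.05, normal approximation.

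With no exclusions, SE = 2 × √(2/26) = 0.555 and power for a 1.0-point difference = Φ(1/0.555 − 1.96) = 43.8%.

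*(a) Contraindicated subgroup, dropped only if in pain.* Let a share f be affected and dropped when trigger pain is at least c = 4. Trigger pain has the same mean and SD as the 72-hour score and correlation ρ with it. With z = (c − μ)/SD and p = 1 − Φ(z), the retained mean is [μ − f(μp + ρ·SD·φ(z))]/(1 − fp), and the number dropped is 26fp.

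Worked case, f = 0.20, ρ = 0.5:
- Control: z = 0, p = 0.5, retained mean = (4 − 0.2 × 2.399)/0.9 = 3.911, dropped 2.6.
- PBM: z = 0.5, p = 0.3085, retained mean = (3 − 0.2 × 1.278)/0.938 = 2.925, dropped 1.6.
- Difference 0.986; SE = 2 × √(1/23.4 + 1/24.4) = 0.579; power 39.9%.

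| f | Dropped, control / PBM | Difference, ρ = 0.3 | ρ = 0.5 | ρ = 1 | SE increase |
|---|---|---|---|---|---|
| 0.05 | 0.65 / 0.40 | 0.998 | 0.997 | 0.995 | 1.0% |
| 0.10 | 1.30 / 0.80 | 0.997 | 0.994 | 0.989 | 2.1% |
| 0.20 | 2.60 / 1.60 | 0.992 | 0.986 | 0.973 | 4.3% |

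Varying the means (3/2, 4/3, 5/4), SD (2 or 2.5) and cut-off (4 or 7) gives 0.974-1.007 at ρ = 0.5 and 0.948-1.014 at ρ = 1. The range crosses 1.0, so even the direction is not fixed.

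*(b) Same subgroup, all dropped regardless of pain.* The expected difference stays at 1.0. SE rises by 1/√(1 − f) − 1, which is 2.6% at f = 0.05 and 11.8% at f = 0.20. This costs precision without bias.

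*(c) Everyone the rule could reach, by pain.* Suppose any patient with trigger pain of 7 or more, the protocol's severe band, takes another drug and is dropped (f = 1, c = 7). Then p = 1 − Φ(1.5) = 0.067 in control and 1 − Φ(2) = 0.023 in PBM, so 1.7 and 0.6 patients go. A true 1.0 appears as 0.92 (ρ = 0.5) or 0.87 (ρ = 0.8), and power falls to 36.5% or 33%. This is a stress case, because the protocol directs severe pain to the two named drugs.

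*(d) A single decision.* Dropping one patient scoring 10 from an arm of 26 with mean 4 gives (26 × 4 − 10)/25 = 3.76, a shift of 0.24 points against an SE of 0.555. A rank test would be less sensitive to such a value. How discretion would actually be used cannot be modelled.

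**The case against.** The strongest reply is that the rule will rarely operate and, when it does, may be harmless. Its sentence directly follows the one on contraindications, under a heading about dismissal. A natural reading is that it covers substitutions made in the chair, before any pain score, where exclusion follows a baseline trait. Severe pain is kept on the same two drugs, so stronger pain does not by itself trigger exclusion. The reason must be documented, which gives an audit trail.

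Most of this stands as a limit on size. It does not remove the point. The sentence is not confined to substitutions at dismissal and reaches another drug given for any reason. Documenting the reason does not keep the score in the analysis. Even for substitutions, it is left open which patients are dropped.

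Stronger readings that a reader might infer are not supported:
- *That failing to screen for contraindications is itself a defect.* No eligibility item covers them; the nearest are "Patients at risk for delayed or compromised wound healing" and "Bone marrow transplant or other organ transplant patients who are on chemical immunosuppressants". But contraindication is a baseline trait, and enrolling such patients does not bias a comparison that keeps their scores.
- *That every patient who departs from the two-drug regimen is dropped.* The rule needs another drug to be given. A patient who takes one named drug, or none, is not clearly caught.
- *That exclusions will be made unblinded or to favour PBM.* The documents do not say who decides; the gap is the absence of a rule.
- *That the bias is large.* Attenuation from 0.78 SD to 0.70-0.53 SD can be obtained, but only by assuming that 10-30% of controls are excluded for higher pain. Nothing in the documents suggests such rates.

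**Conclusion.** The point holds as a weakness in the exclusion rule: scores from randomised, treated patients can be removed at undefined discretion, and the analysis text does nothing to offset this. Bias arises where the other drug is taken because of pain. Where it is substituted at dismissal, the main cost is precision, provided the exclusion does not depend on anyone's judgement.

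The size cannot be determined from the documents and is probably small. Illustration (a), with differences of 0.997-0.986 at correlation 0.5, covers only an assumed contraindicated subgroup of 5-20%. Illustration (c) covers everyone the rule could reach but ignores the advice that keeps severe pain on the named drugs. Both rest wholly on assumed prevalence, means, SD, cut-off and correlation. This is a low-priority change, worth making because it removes an avoidable source of selection at almost no cost.

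**What to change.** In Patient Dismissal, replace the clause that permits exclusion with a rule to this effect: *All randomised patients' available VAS scores stay in the primary (72-hour) and secondary analyses in their assigned group, whatever analgesic is taken. Use of any other analgesic is recorded with drug, dose, time and reason. One prespecified sensitivity analysis omits scores recorded after another analgesic was taken.*

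The omission belongs only in the sensitivity analysis, because it selects on pain in the same way as the present rule. Worst-rank scoring should not be used where a drug was substituted for a contraindication: a patient with mild pain and an allergy would be counted among the worst outcomes in the trial.

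A check for contraindications before randomisation is optional. It would make analgesia more uniform but narrow the population slightly.

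The cost is one replacement sentence, one extra analysis, and a line in the diary or call script for the time of intake, which is not clearly requested now. Drug, dose and reason are already to be captured. The downside is some analgesic heterogeneity in the primary analysis, so the result describes pain under the assigned treatment together with whatever analgesic was taken.
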